Title: Web-Based Communication Education for Breast Cancer Survivorship Care

Date approved by Georgetown University Institutional Review Board: 1/30/2017

NCT Number: N/A

Statistical Analysis Plan

The LA Registry has approximately 1,209 Chinese women (age 18-85) who were diagnosed with stage 0-III breast cancer from 2012 through 2014. About 77% (n= 931) are Chinese-speaking immigrants per our preliminary data. Assuming a 28% response rate derived from our prior participation rate (35%) and 80% of the sample expressing interest in a web intervention, we expect approximately 261 women will provide consent for participation. Thus, it is highly feasible to achieve our accrual goal of 118 participants. Chinese American breast cancer incidence rates are increasing meaning that the number of potential participants from the LA Registry should increase.

For Aim 2, assuming that the intervention will increase Chinese survivors' mean communication score from 32 (SD=5.7) to 35.5 points, closer to the NHW's mean score=37 (SD=4.4), we will need a final sample of 90 to detect the 3.5 point difference between the two study groups (n=45 per group, a 1:1 ratio; 80% power, 2-sided, $p<.05$) after accounting for a 10% attrition rate and 85% of women visiting doctors at T2. With 90 women, we will also be 80% powered to detect an increase in perceived control and self-efficacy with Cohen's (d) =0.65 and 0.6, respectively. For Aim 3, we are aware that some women may just visit their doctors at the T2 follow-up. Thus, this pilot trial may not show significant changes in distal outcomes. Moreover, the final 90 women who complete the T2 assessment will allow for detection of a clinically meaningful increase in the PROMIS physical function baseline T score from 48 to 53 points (d=0.6, 80% power, 2-sided, $p<.05$). In this pilot trial, we are not powered to detect modest effect sizes; however, one of the central goals of this R21 study is to obtain data to determine the likely effect sizes for a larger RCT.

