Title: Web-Based Communication Education for Breast Cancer Survivorship Care

Date approved by Georgetown University Institutional Review Board: 1/30/2017

NCT Number: N/A

Study Protocol

1. Purpose of project:

This two-phase research plan will develop and test a culturally relevant, web-based patient education program, hereafter known as E-Talkcare. The intervention aims to empower Chinese cancer patients to effectively communicate with different providers in different healthcare settings.

2. Study design (for example, hypothesis, research questions, standard and experimental procedures/drugs/devices or equipment, etc.):

Our specific aims are to: 1) develop and test the usability and acceptability of a web-based intervention called E-Talkcare for Chinese immigrant breast cancer survivors using qualitative interviewing and analysis; 2) assess the efficacy of the E-Talkcare intervention in enhancing Chinese immigrant survivors' communication competence, perceived control, and self-efficacy in cancer care communication (intermediate outcomes) relative to the usual care control arm, and 3) obtain preliminary data on the efficacy of the E-Talkcare intervention (vs. usual care) in improving patient-reported symptoms, adherence to breast cancer survivorship care guidelines, and quality of life (QoL) (distal outcomes) and explore the mediating role of the intermediate outcomes on distal outcomes. The study includes two phases: 1) conduct qualitative research to develop the E-Talkcare intervention and 2) conduct a pilot RCT to examine the efficacy of the intervention (vs. usual care).

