
To ensure E-Talkcare is user-centered, we will conduct usability tests after "wireframes" (schematics showing information elements and page flows) are produced and the majority of development work is completed. We will invite 5-7 Chinese immigrant breast cancer survivors to participate in a 60-minute one-on-one session. This sample size is generally considered sufficient for uncovering about 80% of the usability issues. During the session, they will be given specific tasks to complete using the system and asked to talk aloud as they perform the tasks. Our RA will record how the tasks are completed (or failed). Right after the session, they will complete the System Usability Scale (SUS). An overall SUS score of 70 or above will be considered as acceptable usability. These test results will lead to modifications of ETalkcare. Next, we will ask the same survivors to take the second usability test to inspect if the problems have been fixed and then complete a perceived usefulness and acceptability questionnaire. Participants will be enrolled from the DC area, using the methods for the qualitative interview recruitment above. In Phase II, a pilot pre-post-test RCT will be conducted to test the efficacy of the intervention. Recruitment: We will enroll 118 eligible Chinese cases from the LA cancer registry. On

average, it takes 6 to 12 months after diagnosis for a case to be reported to the registry. Most cases will have completed treatment by the time they are initially contacted. Cases will be randomly selected from a list of potentially eligible cases. [name] at the LA registry will lead the identification of cases and send them to the PI. An RA at GU will mail an invitation letter to the cases, which will describe how the patient was identified, study objectives, and patient eligibility, involvement, and rights. It will include a self-addressed stamped response form for patients to opt in or out of this study. The RA will call women to answer questions and obtain consent if the response form is not received 10 days after mailing. In this call, the RA will ascertain patients' race/ethnicity and recurrence status. Those with multiple races will be excluded.

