The secondary objective is to obtain preliminary data on the efficacy of the E-Talkcare intervention (vs. usual care) in improving patient-reported symptoms, adherence to breast cancer survivorship care

guidelines, and quality of life (QoL) and explore the mediating role of the intermediate outcomes on distal outcomes.

6. Inclusion criteria:

Eligible Chinese women must be: 1) \geq age 18, 2) foreign-born speaking Mandarin and/or Cantonese, 3) diagnosed with breast cancer at stage 0, I, II or III, 4) 1-3 years post-diagnosis and completed primary treatment (surgery, radiation, and chemotherapy), and have 5) no recurrence, and 6) internet access.

7. Exclusion criteria:

Women with other cancer types are ineligible due to different treatment complications. Women in Phase I will not be eligible for Phase II.

8. Treatment Plan:

View a website which includes three web modules: 1) Culture and autonomous communication, 2) Online symptom reporting and questions, and 3) Question database and prompt lists. The first module will educate Chinese women about the US values of patient autonomy and how to actively help providers understand their needs in order to make personalized care plans. Second, intervention women will report the PROMIS symptoms and QoL variables monthly during the 3-month intervention period and post their top three symptom questions (either in English or Chinese) on the web. Third, all questions will be anonymously collected and posted on the web by topic (e.g., fatigue and pain). Using this question database, women can build a QPL relevant to their conditions and needs for medical visits within the study period. Using QPL helped patients actively engage in clinical communication.

9. Please state the relative importance/value of the trial, considering standard therapy and competing trials:

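### Does the 1-3 year eligibility window undermine the SAP's accrual estimate, which is built on 2012-2014 diagnoses?

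*SAP*

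**What the plan says.** The opening paragraph of the SAP counts "approximately 1,209 Chinese women (age 18-85) who were diagnosed with stage 0-III breast cancer from 2012 through 2014" in the Los Angeles registry. It takes 77% of them as Chinese-speaking immigrants (931) and applies a 28% response rate, itself 35% prior participation times 80% interest in a web intervention. From this, "we expect approximately 261 women will provide consent for participation", and the paragraph concludes that "it is highly feasible to achieve our accrual goal of 118 participants". It adds that the pool should grow because incidence is rising, but gives no figure.

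Protocol section 6 (Inclusion criteria) requires women to be "1-3 years post-diagnosis and completed primary treatment (surgery, radiation, and chemotherapy"). Protocol section 2, under Recruitment, says "Cases will be randomly selected from a list of potentially eligible cases" and that on average "it takes 6 to 12 months after diagnosis for a case to be reported to the registry".

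On timing, the SAP title block reads "Date approved by Georgetown University Institutional Review Board: 1/30/2017", and the protocol carries the same date. Protocol section 2 places the trial after the development work: "The study includes two phases: 1) conduct qualitative research to develop the E-Talkcare intervention and 2) conduct a pilot RCT". Neither document states when Phase II enrolment starts or how long it lasts.

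**The concern.** The accrual calculation never applies the time-since-diagnosis criterion. Taking the approval date as the earliest possible contact date, every woman diagnosed in 2012 or 2013 is already more than three years out, along with those diagnosed in the first weeks of 2014. None of the group can come into the window later, because its last member passed one year by 31 December 2015.

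The 261 is the only quantified support for the feasibility statement. If it mostly counts women whom the trial's own rule excludes, a reader could fear that 118 is out of reach, or that invitations would go mainly to ineligible women. A shortfall would matter, because 118 is what delivers the 90 analysable women assumed in the power calculation: 118 x 0.90 x 0.85 = 90.3.

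**Working it through.** **Inputs.** From the SAP: 1,209 cases over three diagnosis years, 77%, 35%, 80%, target 118. From protocol section 6: the 1-3 year window. From the title blocks: 30 January 2017. Assumptions: diagnoses evenly spread over 2012-2014, the same case rate afterwards, and contact no earlier than the approval date.

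**1. The SAP's figure.**
- 1,209 x 0.77 = 930.9 (stated 931)
- 0.35 x 0.80 = 0.28
- 931 x 0.28 = 260.7 (stated 261)

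The multiplication is correct. Consents per registry case are 0.77 x 0.28 = 0.2156.

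**2. The 2012-2014 group alone, at 30 January 2017.** In-window diagnoses run from 30 January to 31 December 2014.
- 336 / 1,096 days = 30.7%, so about 69% are out of window
- 1,209 x 0.3066 = 371 women
- 371 x 0.77 = 285 immigrants
- 285 x 0.28 = about 80 consents

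With the 1-2% annual growth mentioned in protocol section 3, this becomes 81-82. The group yields none from 1 January 2018. These are the figures that make the concern look serious.

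**3. The pool the protocol actually samples.** Recruitment draws on potentially eligible cases, and eligibility is a moving two-year window. The implied rate is 1,209 / 3 = 403 cases a year.

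| Accrual length | Diagnosis span | Cases | Consents (x 0.2156) |
|---|---|---|---|
| Single date | 24 months | 806 | 173.8 |
| 6 months | 30 months | 1,007.5 | 217.2 |
| 12 months | 36 months | 1,209 | 260.7 |

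The 6-12 month average reporting lag does not empty the recent end of the window: on average a case is registered by the time it reaches one year.

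**4. Margin over 118.**
- Cases needed: 118 / 0.2156 = 547, or 547 / 403 = 1.36 years (about 16 months) of diagnoses. The window holds 24.
- Break-even response rate at a single date: 806 x 0.77 = 621 immigrants; 118 / 621 = 19.0%, against 28% assumed.
- Further loss tolerable at a single date: 1 - 118 / 173.8 = 32%. Over 12 months: 1 - 118 / 260.7 = 55%.

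**5. Why three diagnosis years.** A two-year window plus 12 months of accrual spans exactly three years of diagnoses. A 2012-2014 range fits a calendar-2015 accrual period. Moving the years forward at the same case rate returns 261.

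**The case for a change.** The strongest reply is that a moving eligibility window cannot be turned into a yield without a start date and an accrual length, and the documents give neither. The figure of 261 holds only if accrual lasts about 12 months. At a single date the margin over 118 falls from 2.2-fold (261 / 118) to 1.5-fold (174 / 118), and the break-even response rate rises from 12.7% (118 / 931) to 19.0%. The 174 also takes no deduction for recurrence, incomplete primary treatment or multiple race, for which no rates are given. The SAP's remark about rising incidence does not repair this, because growth of 1-2% a year barely moves the numbers.

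Much of that stands. The years are out of date on the natural reading, since Phase I is written in the future tense under a 2017 approval, and the headroom is less certain than the SAP's tone suggests. What does not stand is the step to a wrong cohort. No text confines recruitment to women diagnosed in 2012-2014, so the 80 consents and the fall to zero in 2018 describe a plan that was not written. Nor do the documents contain a registry request with a fixed diagnosis range that would need correcting. The remaining uncertainty concerns the size of a comfortable margin and does not put the target in doubt.

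**Conclusion.** The inconsistency between the SAP's accrual paragraph and protocol section 6 is genuine but clerical. A team following the plan as written would request potentially eligible cases, apply the 1-3 year criterion at contact and enrol only eligible women. On the SAP's own rates that pool supports about 174 consents at one date, 217 over six months and 261 over a year, against 118.

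This rests on an even spread of diagnoses, a case rate of 403 a year continuing after 2014, and the SAP's 77% and 28%. The 69% loss from the 2012-2014 group further assumes that contact began no earlier than 30 January 2017. Had screening preceded about July 2016, most of that group would still have been eligible.

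Fresh diagnosis years would tidy a background paragraph. They would leave the target, power, randomisation, analysis and feasibility conclusion where they are, and possibly the 261 as well. No change to the plan is called for.

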will shoot three culturally tailored videos (~4 minutes each) to model how Chinese survivors can seek, provide, and verify information (three essential communication skills) to remedy the three communication issues: 1) encouraged them to ask cancer-related questions, 2) ensured that they understood all the information doctors provided, and 3) provided sufficient information. We will incorporate culturally relevant messages into the scripts. For example, a script will portray a cultural practice where Chinese patients tend not to ask questions as a sign of respect when they observe that their doctors have limited time. The video will be shot to contrast passive and active communication by presenting the following scenarios, for example: a) a doctor did a quick examination and left before a Chinese survivor had a chance to ask questions (passive, Chinese style); b) the survivor calls her doctor back and asks if s/he can give her a few more minutes to know what exam was done and its results (active, autonomous style). Drafted scripts will be based on breast cancer survivors' stories from our prior research and revised iteratively based on the focus group, individual interviews and CAB reviews. The videos will be available in Chinese and English, similar to our Chinese mammography video. Second, intervention women will report the PROMIS symptoms and QoL variables monthly during the 3-month intervention period and post their top three symptom questions (either in English or Chinese) on the web. Researchers and CAB members will then review and refine the three questions if necessary. For symptom questions derived from specific treatment (surgery, radiation, and adjuvant therapy), we will consult with our clinicians in their specialty areas before providing women with suggested questions posted online within a week. For questions posted in Chinese, we will use Google translate to provide English translations via a link. Our bilingual research assistant (RA) will review and modify the translations as needed. Then, we will mail the women their bilingual symptom reports and an individualized QPL (both can also be printed at home) for use during medical visits. Third, all questions will be anonymously collected and posted on the web by topic (e.g., fatigue and pain). Using this question database, women can build a QPL relevant to their conditions and needs for medical visits within the study period. Using QPL helped patients actively engage in clinical communication. In this website, didactic information (text, image, video formats) and interactive elements (reporting symptoms with open-ended comments, posting and reading questions) will be incorporated throughout. A culturally adaptive interface and content will be written and designed based on our formative work in phase I. To enhance accessibility among individuals with limited computer literacy, most pages will include audio narration of the content. Clear written instructions will walk these users through a linear trajectory.

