Randomization: After the baseline interview, participants will be randomly assigned to 1) E-Talkcare or 2) usual care in a 1:1 ratio. We will conduct variable permuted block randomization, using three block sizes of 2, 4, and 6, and run simple randomization in each block. This method can minimize the risk of imbalance due to unexpected enrollment shortfalls and facilitate planning and implementation of the intervention delivery. A RA who will not be one of our interviewers will assist the randomization.

Intervention delivery: After randomization, we will mail women in the intervention group the E-Talkcare web address, a user name, and a temporary password. Once a user signs in, she will be able to read or listen (through audio narration) to instructions on how to complete the intervention in order, though she can freely navigate between web modules. Each module will have an ever-present indicator (showing users' progress) and a link to for users to continue navigating through modules. We will design the full intervention to be about 30 minutes and able to complete with one visit as some women may not return to the webpage. For women with problems accessing the website, our RA will walk them through the website via telephone or ask our current community partners in the LA area to assist.

Elderly Chinese are usually taken care of by family members per our project experience who will be able to assist our older participants in accessing E-Talkcare. Per our data, about 60% of Chinese survivors visit their follow-up care doctors within 3 months and 93% within 6 months, consistent with the NCI report and recommended breast cancer care guidelines. We will ask participants to complete the full intervention within 3 months after intervention delivery and then complete a 3-month post-randomization interview (T1). The website will remain open for six months after intervention delivery to allow participants to use QPL if they wish. A 6-month post-randomization interview (T2) will then be administered.

Usual care: Survivors randomized to the usual care group will receive care from their doctors as usual, allowing us to compare the intervention against real-world practice to inform next steps. Since we do not know if the intervention will be efficacious, we decided not to provide a delayed intervention to control participants

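### The SAP's 90 is net of dropouts and women without a doctor visit, but Aim 3 calls it the T2 completers, who would number about 106; no analysis set is stated

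*SAP*

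**What the plan says.** For Aim 2, the SAP plans 90 women (45 per group) to detect 3.5 points on the communication score, SD 5.7, with 80% power at a two-sided 5% level. It presents that number as what is needed "after accounting for a 10% attrition rate and 85% of women visiting doctors at T2". Enrolment is given as an "accrual goal of 118 participants", and the Protocol (section 2, Phase II recruitment) agrees: "We will enroll 118 eligible Chinese cases from the LA cancer registry".

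For Aim 3, the SAP says that "the final 90 women who complete the T2 assessment" suffice to detect a rise in "PROMIS physical function baseline T score from 48 to 53 points", at d = 0.6 and 80% power.

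In the Protocol (section 2, Randomization), "participants will be randomly assigned to 1) E-Talkcare or 2) usual care in a 1:1 ratio". Under Intervention delivery, T2 is an interview six months after randomisation, with no stated condition that the woman has seen a doctor. The same paragraph puts follow-up visits at 60% of survivors within 3 months and 93% within 6 months.

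Neither document names an analysis set or says how women without a visit are handled.

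**The concern.** One number is attached to two groups. In the accrual arithmetic, 90 is what remains after removing dropouts and then women who did not see a doctor. Under Aim 3 it is everyone who completes T2. The second group contains the first and is larger.

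What is at stake is the analysis set. Seeing a doctor happens after randomisation, and an intervention designed to prepare women for medical visits could plausibly change who goes. A comparison restricted to visitors would therefore not be protected by the randomisation. The SAP says that "one of the central goals of this R21 study is to obtain data to determine the likely effect sizes for a larger RCT". An effect among visitors and an effect among all randomised women are different quantities, and the planner of the next trial needs to know which one was estimated.

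**Working it through.** **Inputs.** From the SAP: 118 enrolled; 90 final (45 per group); 10% attrition; 85% visiting doctors at T2; 3.5 points with SD 5.7; d = 0.65 (perceived control) and 0.6 (self-efficacy); 48 to 53 T-score points at d = 0.6. From the Protocol, section 2: 93% visiting within 6 months.

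**1. Reproducing the plan's figures.**
- Both allowances: 90 / (0.90 x 0.85) = 117.6, which rounds up to 118. In reverse, 118 x 0.90 x 0.85 = 90.3.
- Attrition only: 118 x 0.90 = 106.2.
- Visits only: 118 x 0.85 = 100.3.
- Power basis: d = 0.6 needs 44.6 per group by the two-sample t-test, so 45. The ratio 3.5/5.7 = 0.614 needs 43.

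The SAP does not print the multiplication, but of its two allowances only both together connect 118 to 90.

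**2. T2 completers.** At 10% attrition they number about 106, or 53 per group. For 90 to be the completers, attrition would have to be 1 - 90/118 = 23.7%. Alternatively, at 10% attrition, enrolment would need to be only 90/0.90 = 100.

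**3. Completers without a visit.**
- SAP figure: 106.2 x 0.15 = 15.9, about 16.
- Protocol figure: 106.2 x 0.07 = 7.4, about 7. Completers with a visit would then be 118 x 0.90 x 0.93 = 98.8, about 99.

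**4. Power and precision.** Two-sample t-test, two-sided 0.05, n per group, noncentrality d x sqrt(n/2). For d = 0.614 this is 2.91 at n = 45 and 3.16 at n = 53. The 95% CI half-width is t x 5.7 x sqrt(2/n).

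| Quantity | 45 per group | 53 per group |
|---|---|---|
| Power, 3.5 points at SD 5.7 | 82.1% | 87.9% |
| Power, d = 0.60 | 80.4% | 86.4% |
| Power, d = 0.65 | 86.2% | 91.2% |
| Detectable d at 80% power | 0.597 | 0.549 |
| The same, communication points (x 5.7) | 3.40 | 3.13 |
| The same, PROMIS T-score points (x 8.33) | 4.98 | 4.58 |
| 95% CI half-width, communication | 2.39 | 2.20 |

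The PROMIS SD is the one implied by the SAP: 5/0.6 = 8.33.

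**5. Sensitivity, on an assumption that neither document makes.** Suppose 3.5 points applies only to the 85% who visit and the others gain nothing. The average over all completers is then 0.85 x 3.5 = 2.98 points (d = 0.522), and power at 53 per group is 75.9%.

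**The case against.** The best defence is that 90 is a cautious planning number with a loose label. Enrolment can be inflated for women who will have no visit in which to use the skills, while everyone assessed is still analysed. If 90 women suffice for d = 0.6, so do 106. The SAP's Aim 3 remark that some women may see a doctor only around T2, so that distal outcomes may not move, treats late visiting as dilution among women who stay in the comparison. That remark concerns late visitors rather than non-visitors, so it is only suggestive.

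Much of this stands. A reader might infer that the SAP excludes women without a visit; nothing in it says so, and the harm described is conditional. The 85% may also allow for women who cannot rate communication without a visit. That would explain 90 for the communication score.

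A reader might also cite the Protocol's statement that "intervention women will report the PROMIS symptoms and QoL variables monthly during the 3-month intervention period" as proof that PROMIS outcomes need no visit. It does not show that: it describes a module of the intervention, in one arm, and not the T2 assessment. The support for there being no visit condition is the Protocol's description of the T2 interview, and it is support by silence.

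What the defence does not remove is the mismatch itself. Aim 3 names T2 completers, and at the SAP's own attrition they are not 90. The lack of a stated analysis set also remains.

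**Conclusion.** The SAP's 90 is the wrong count for the group that Aim 3 names. On the stated 10% attrition it should be about 106 (53 per group). This rests on arithmetic from the documents' own figures.

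It would be tempting to conclude that the trial is underpowered. The documents do not support that. With 106 completers the stated 80% power holds with room to spare, provided the stated effects are averages over all women analysed. The 76% figure for communication depends on a dilution assumption that is ours, and the 88% depends on the opposite one, with every completer having a communication score.

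The practical risk is confined to the analysis. If the 90 were taken as the analysis set, about 7 to 16 assessed women would be left out on a post-randomisation event, depending on whether 93% or 85% visit. The point is worth fixing because the pilot's effect sizes are meant to be reused.

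**What to change.** 1. Restate expected T2 completers as about 106 (53 per group), with 80% power for d = 0.55, or about 4.6 T-score points for PROMIS physical function at the implied SD of 8.3.
2. State that Aims 2 and 3 compare all randomised women with outcome data, in the arm assigned, whether or not they visited a doctor. Keep any visitors-only comparison descriptive.
3. Say what the 85% is for. If it allows for women who cannot rate communication without a visit, limit it to that score, keep 45 per group there, and report the number unrated by arm. Otherwise, give power for 3.5 points as about 88% if that is the average over all completers, beside about 76% if it applies only to the 85% who visit and the rest gain nothing.
4. Reconcile the SAP's 85% with the Protocol's 93% within six months.

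The cost is SAP wording: no extra patients, visits or data. For outcomes measured in all completers, the 95% CI is about 8% narrower than with 90 women (2.20/2.39 = 0.92). That gain does not apply to communication if only visitors can be scored.
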